7.9 MISSING DATA AND SENSITIVITY ANALYSIS

Regarding endpoints involving acute GVHD response to study treatment (overall response, DOR, GVHD-free survival, acute GVHD response, organ-specific response), any patient with a missing acute GVHD assessment at the evaluation day will be classified as a non-responder (NR) at that time point.

For the duration of response (DOR), a patient with a missing acute GVHD assessment will be considered as a failure at that time point.

For GVHD-free survival, a patient with either a missing acute or chronic GVHD assessment will be considered as a failure at that time point.

For time-to-event outcomes other than DOR and GVHD-free survival (NRM, OS, PFS, chronic GVHD, relapse/progression), patients that withdraw or are lost to follow-up are assumed to be censored at random.

For other endpoints, the occurrence of missing data, whether due to the patient’s missing assessment(s) or withdrawal from the study, is assumed to occur randomly.

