3.2 Secondary Endpoints

3.2.1 Duration of Response (DOR)

The duration of response (DOR) is defined as time from the Day 28 response (CR or PR) to any of the following events: recurrence/progression of acute GVHD, new systemic salvage therapy for

acute GVHD, re-escalation of steroids to greater or equal to 2.5 mg/kg prednisone or equivalent, or death from any cause. Patients without any of these events will be censored at last follow up. DOR will be evaluated at 6- and 12-months post-randomization.

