5.7 Analysis of Secondary Endpoints

5.7.1 Duration of Response

Duration of response will be evaluated at 6- and 12-months post-randomization in the cohort of patients who achieve a Day 28 response. There will be a primary and secondary analyses of DOR. In the primary analysis, DOR is defined as the time from Day 28 response to progression, new salvage therapy for acute GVHD, death from any cause, or re-escalation of steroids to ≥ 2.5 mg/kg prednisone or equivalent. Patients without any of these events will censored at last follow up. For the secondary analysis, DOR will be defined as time from Day 28 response to death from any cause or new salvage therapy. Otherwise, patients are censored. For each definition, the probabilities of DOR will be estimated using the Kaplan-Meier method and compared between treatment arms using the log-rank test.

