6.3.1 DURATION OF RESPONSE (DOR)

DOR is defined as the time from Day 28 response (CR or PR) until the first of the following events occurs: progression of acute GVHD, death, any next-line GVHD therapy, or escalation of prednisone-equivalent steroid dose to 2.5mg/kg/day or more. DOR will be evaluated in the set of patients that attain a response (CR or PR) on Day 28. Progression is defined as the worsening by one stage or more from nadir in any acute GVHD target organ without improvement in other organs in comparison with the prior response. In the DOR context, the prior response refers to Day 28 response (CR or PR); nadir in an organ refers to Day 28 stage of this organ. For a patient in CR at Day 28, nadir is stage 0 in all target organs.

DOR, in days, is calculated as (Date of acute GVHD progression, death, next-line acute GVHD therapy, escalation of prednisone-equivalent steroid dose to 2.5mg/kg/day or more, or last known to be alive) – (Date of Day 28 Response) +1.

Table 7: DOR Definition

Situation	Date of Event or Censoring	Outcome
Death, acute GVHD progression, next-line acute GVHD therapy initiation, or steroid dose escalation $\geq 2.5\text{mg/kg/day}$ before or on analysis cutoff date	Date of event	DOR event
Death, acute GVHD progression, next-line acute GVHD therapy initiation, or steroid dose escalation $\geq 2.5\text{mg/kg/day}$; all events happened after analysis cutoff date	Analysis cutoff date	Censored
No event occurred, last known date alive is before or on analysis cutoff date	Last known date alive	Censored
No event occurred; last known date alive is after analysis cutoff date	Analysis cutoff date	Censored

DOR = Date of Event or Censoring – Date of Day 28 Response + 1

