7.5 ANALYSIS OF SECONDARY ENDPOINTS

7.5.1 DURATION OF RESPONSE (DOR)

DOR will be evaluated in the set of patients in the ITT population who achieve a response (CR/PR) at Day 28. DOR will be estimated using the Kaplan-Meier estimator, with the probability of having a durable response, i.e. retaining the CR/PR, evaluated at 6 and 12 months post-randomization. Estimates and 95% CIs for the median and quartiles of the DOR will be obtained from the Kaplan-Meier estimator using the inverse Kaplan-Meier method described in Andersen et al. 1993. DOR will be compared from Day 28 to 12 months post-randomization between arms using a log rank test. DOR will also be displayed graphically using Kaplan-Meier curves with numbers of subjects at risk at specific time points presented for each treatment group.

Primary and supplementary analyses will be performed. In the primary analysis, DOR is defined as stated in section 6.3.1, as the time from Day 28 response to progression of acute GVHD, any next-line GVHD therapy, escalation of prednisone-equivalent steroid dose to 2.5mg/kg/day or more, or death from any cause. Its estimand is displayed in **Table 18**. The clinical question of interest is: what is the difference in duration of response between AAT combined with corticosteroids versus PTM combined with corticosteroids in patients with high risk acute GVHD following allogeneic HSCT who attain a Day 28 overall response, regardless of discontinuation of study treatment?

Table 18: Estimand for Duration of Response - Primary Analysis

Estimand Attribute	Definition		
Variable	Duration of Response; refer to Sections 6.3.1 and 7.9, and above for details		
Treatment	AAT (+corticosteroids) or PTM (+corticosteroids), refer to Section 2.1 for details		
Population	Patients with high risk acute GVHD following allogeneic HSCT who attain a Day 28 overall response		
Intercurrent Events	Event	Strategy	Description

Estimand Attribute	Definition		
	1. Acute GVHD progression	Composite strategy	Classified as an event
	2. Death	Composite strategy	Classified as an event
	3. Initiation of additional systemic aGVHD treatment ¹	Composite strategy	Classified as an event
	4. Discontinuation of study treatment	Treatment policy	No effect on variable
Population-level Summary	Median and quartiles with 95% CIs for each arm; probabilities of durable response at 6 and 12 months by arm; log rank test p-value comparing arms from Day 28 to 12 months post-randomization		

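### SAP 7.9 counts a missed acute GVHD assessment as a duration-of-response failure, against the protocol and SAP Table 7 and undeclared in 7.11; for the supplementary DOR the rule is wrong as written

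*SAP*

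**What the plan says.** SAP 7.9 treats DOR as one of the acute GVHD response endpoints, for which a patient with a "missing acute GVHD assessment at the evaluation day will be classified as a non-responder (NR) at that time point". A separate sentence on DOR then says that "a patient with a missing acute GVHD assessment will be considered as a failure at that time point". The censoring sentence that follows begins "For time-to-event outcomes other than DOR and GVHD-free survival", so DOR is expressly left out of it.

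The protocol says otherwise. Section 3.2.1 lists the DOR events as recurrence or progression of acute GVHD, new systemic salvage therapy, steroid re-escalation and death, and continues: "Patients without any of these events will be censored at last follow up". Section 5.7.1 repeats this for the primary definition ("Patients without any of these events will censored at last follow up"). For the second definition, whose events are death and new salvage therapy, it ends: "Otherwise, patients are censored".

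SAP 6.3.1 lists progression, death, next-line therapy and steroid escalation. Table 7 has a row "No event occurred, last known date alive is before or on analysis cutoff date", and such a patient is censored at the last known date alive. It has no row for a missed assessment.

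The SAP's DOR estimand points to both places. Table 18 defines the variable as "Duration of Response; refer to Sections 6.3.1 and 7.9, and above for details", and Table 19 (supplementary DOR) gives the same two references. SAP 7.11 names one change from the protocol's analysis, the significance level for exploratory endpoints, and says that it is the only one.

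**The concern.** The same patient is censored under one section and has an event under another, and the estimand tables cite both. If 7.9 is the intended rule, the SAP departs from the protocol's censoring without declaring it, and the statement in 7.11 is inaccurate.

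The rule also cannot be programmed as it stands. Seven acute GVHD assessments follow Day 28 (Days 35, 42, 49, 56 and 86, then 6 and 12 months; Protocol Table 4-1), and 7.9 does not say which of them are evaluation days for DOR. SAP 6.2, 6.3.5 and 6.3.6 treat an out-of-window assessment as missing; 6.3.1 is silent.

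At stake is the confirmatory sequence in SAP 7.1. The primary and supplementary DOR are tests 2 and 3. If either is not significant, NRM, OS, PFS and GVHD-free survival are not tested confirmatorily. No sensitivity analysis of the DOR missing-data rule is specified.

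**Working it through.** **One patient under each rule.** A responder misses Day 42, attends every other visit, and is alive with no listed event at Day 365.

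| Source | Result |
|---|---|
| Protocol 3.2.1, 5.7.1 | censored at last follow-up |
| SAP 6.3.1, Table 7 | censored at last known date alive: 365 − 28 + 1 = 338 days |
| SAP 7.9, if Day 42 counts | event on Day 42: 42 − 28 + 1 = 15 days |

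**Supplementary DOR.** Patient A attends Day 42 with documented progression, and has no next-line therapy and no steroid escalation. Table 19 gives progression no effect, so A is still event-free. Patient B misses Day 42 and has no event. Under 7.9, B fails. An unknown GVHD stage therefore counts for more than a known worsening. GVHD stage is not an event in this definition, so there is nothing to impute.

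**Size for the primary DOR.** The documents state no power for DOR. Inputs from Protocol 5.2 are 68 per arm and response of 50% versus 75%. A pooled two-sample Z test at one-sided 2.5% gives 86.2%, which reproduces the stated 86%. Expected responders are 68 × 0.50 = 34 (PTM) and 68 × 0.75 = 51 (AAT), 85 in total. Follow-up from Day 28 to Day 365 is 337 days, and the test is a two-sided 5% log-rank.

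The assumptions, none of them in the documents, are exponential DOR, 12-month durability of 50% versus 75% or 60% versus 80%, and a 5% chance that a responder misses one randomly chosen visit, independently of GVHD course. The 5% is the ceiling of the under-5% missing data expected in Protocol 5.5.3.

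Added events equal 0.05 times the expected number event-free at 12 months:
- 50% vs 75%: 34 × 0.50 + 51 × 0.75 = 55.25; × 0.05 = 2.76 (simulated 2.77 and 2.78)
- 60% vs 80%: 34 × 0.60 + 51 × 0.80 = 61.2; × 0.05 = 3.06 (simulated 3.06)

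Simulated power, 30,000 trials per row:

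| Durability | Visits that count | Censoring | Missing-as-failure | Decisions that differ |
|---|---|---|---|---|
| 50% vs 75% | all seven | 68.4% | 61.1% | 13.0% |
| 50% vs 75% | 6 and 12 months | 67.9% | 63.5% | 9.6% |
| 60% vs 80% | all seven | 53.6% | 46.2% | 14.7% |
| 60% vs 80% | 6 and 12 months | 54.0% | 48.6% | 12.0% |

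With 2% to 3% of responders missing a visit (50% vs 75%), the loss is about 2 to 5 points and about 5% to 10% of decisions differ.

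**The opposite mechanism.** Now let missed assessments belong to true failures: 10% or 20% of failing responders (an assumption) are never assessed as failing but are known to be alive. At 50% versus 75%, full-data power is about 68%. Censoring at last known date alive gives about 61% or 54%. Missing-as-failure stays at about 68%.

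**The case against.** The best defense is that 7.9 is deliberate and governs. It names DOR specifically, removes it from the censored outcomes, and is cited in Tables 18 and 19. It matches the handling of the primary endpoint, GVHD-free survival and the response endpoints, where a missed assessment is also a failure. The protocol does not define last follow-up or mention missed assessments, so 7.9 could be called an elaboration. On this view the defect is one absent row in Table 7.

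Much of this stands. 7.9 is probably the intended rule, and missing-as-failure is a recognized choice for the primary DOR. A reader might infer that 7.9 is simply wrong there and must give way to censoring. The documents do not support that: which rule loses power depends on why assessments are missed, and neither document says. Censoring at last known date alive has its own weakness, because a patient who worsens unseen is counted as still responding.

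The defense fails on two points. An elaboration that turns a patient the protocol censors into an event is a change, and 7.11 denies any such change. And consistency with other endpoints cannot justify the rule for the supplementary DOR, where GVHD stage plays no part.

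A reader might also infer a large loss of power by applying 5% to each of seven visits. The protocol's figure is an overall expectation, not a per-visit rate, and the 6- and 12-month evaluation times make the two-visit reading plausible.

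**Conclusion.** The point holds as a conflict to reconcile, together with one rule that is wrong as written. SAP 7.9 departs from Protocol 3.2.1 and 5.7.1 and does not match SAP 6.3.1 and Table 7, and 7.11 is inaccurate in not declaring it. The supplementary DOR should not carry the missing-assessment rule at all. For the primary DOR the choice between the rules is a trade-off.

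The size is modest and rests on assumed durability and missingness. At 50% versus 75% durability, 5% uninformative misses cost about 4 to 7 points of power and change about 10% to 13% of decisions; misses tied to true failure reverse the direction.

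A reader might infer that the rule favors AAT. With equal miss rates it mainly dilutes a real difference. With equal 60% durability and 5% of PTM but 1% of AAT responders missing one visit, a significant result for AAT occurs in 4.7% (seven visits) or 4.2% (two visits) of trials, against about 3% with censoring. The documents give no reason to expect that imbalance, and SAP 7.10.2 would show one, since it tabulates missed visits by arm. The Day 28 primary endpoint is not affected, and the DOR tests are reached only if it succeeds.

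**What to change.** Before treatment results are known (SAP section 1 allows revision until the database hard lock):

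1. State in 7.9 that the missing-assessment rule does not apply to the supplementary DOR, and that patients without one of its listed events are censored.
2. For the primary DOR, make 7.9 and Table 7 give one rule. Either censor as the protocol says, defining last follow-up once as the last acute GVHD assessment or as the last known date alive; or keep missing-as-failure, add its row to Table 7, name the visits it covers, say whether an out-of-window visit counts as missing, and declare the change in 7.11.
3. Run the other rule as a sensitivity analysis of the primary DOR, with the same detail on visits and windows.

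The cost is wording in 6.3.1, Table 7, 7.9 and, if the failure rule is kept, 7.11, plus one sensitivity analysis. No new data are needed.

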7.10 ASSESSMENT OF IMPACT OF COVID-19 ON TRIAL RESULTS

7.10.1 COVID-19 RELATED MODIFICATIONS TO DATA COLLECTION

The BMT CTN considers the COVID-19 era to have potentially impacted its trials effective March 10, 2020 unless otherwise specified. Data collection was adjusted, and guidance was given to centers to track the impact of COVID-19. Specifically, the following modifications were made:

- Impact of COVID-19 on scheduled visits: Collection of information about whether visits were missed or scheduled out of the assessment window; the type of visit (clinic visit, telemedicine visit, phone contact, or combination); and if the visit was missed, what the reason for the missed visit was (which included COVID-19 as an option)
- COVID-19 infections: Guidance on the collection of COVID-19 infection occurrences was incorporated into the infection data collection form
- COVID-19 related deaths: Addition of COVID-19 as a potential primary cause of death

7.10.2 COVID-19 RELATED EVENTS AND VISIT DISRUPTIONS

Frequencies and percentages will be provided on the number of missed visits, out of window visits, type of visits, and reasons for missed visits, summarized overall and by treatment arm. The number of deaths attributed to COVID-19 and the number of COVID-19 infections will also be described by treatment arm.

7.10.3 SENSITIVITY ANALYSIS OF THE PRIMARY ENDPOINT

The primary endpoint of this study is overall response (CR+PR) at Day 28 post-randomization. To assess the impact of COVID-19 on the trial's pivotal analysis, the following COVID-19 sensitivity analyses (CA) are proposed.

- CA1: Exclude patients from the analysis who have missing Day 28 GVHD assessments attributed to a COVID-19 related event or for those who have a telemedicine or phone contact visit only
- CA2: Exclude patients from the analysis who had a COVID-19 infection or death attributed to COVID-19 before or on Day 28
- CA3: Exclude all patients who are excluded from analysis in CA1 and/or CA2

For each sensitivity analysis, the primary endpoint will be analyzed as described in Section 7.4.3.1 according to the ITT principle. The purpose of the sensitivity analyses is to assess the robustness of the pivotal analysis results. The impact of sensitivity analysis populations on the number of responses and widths of the confidence intervals should be considered in interpreting these analyses.

If thought to be important based on the results, similar sensitivity analyses of secondary endpoints may also be conducted.

7.11 CHANGES TO PROTOCOL-SPECIFIED ANALYSIS

The current SAP elaborates on the protocol-specified analysis. The sole change in the SAP from the protocol-specified analysis is that the significance level of the two-sided testing of exploratory endpoints is planned to change from 5% to 1%. Any future revisions to the SAP that constitute changes from the protocol-specified analysis, and the justification for these changes, will be documented here.

APPENDIX B: INTERIM ANALYSIS FOR FUTILITY: DSMB DATA PRESENTATION PLAN

Protocol and Primary Endpoint

The primary endpoint for the protocol BMT CTN 1705 “A Randomized, Double-Blind, Placebo-Controlled Multicenter Phase III Trial of Alpha 1 – Antitrypsin (AAT) Combined with Corticosteroids vs Corticosteroids Alone for the Treatment of High-Risk Acute Graft-versus-Host Disease (GVHD) Following Allogeneic Hematopoietic Stem Cell Transplant” is overall response at Day 28. Overall response at Day 28 is defined as having a complete or partial response (CR or PR) at Day 28, i.e. having partial or complete resolution of acute GVHD symptoms in some organ(s) without worsening in any other(s) along with being alive, free of any next-line GVHD therapy, and free of escalation of prednisone-equivalent steroid dose to 2.5mg/kg/day or more. Acute GVHD organ staging at Day 28 is compared to maximum GVHD organ staging within 72 hours prior to enrollment to determine whether a complete or partial resolution has occurred. Organ staging is performed according to MAGIC criteria (Harris et al. 2016). Patients with a missing Day 28 acute GVHD assessment will be classified as non-responders (NR).

Study Design on Interim Analysis

This trial includes one formal interim analysis for futility, to occur once 76 patients are evaluable for the primary endpoint. The primary analysis will be done using the intention-to-treat (ITT) population. The intention-to-treat (ITT) population consists of all randomized subjects, classified according to their randomized treatment assignments.

A logistic mixed model will be used to evaluate the effect of study treatment on Day 28 overall response while accounting for treatment center and MN risk category (high vs. standard), with center-group included as a random effect and treatment arm and MN risk as fixed effects. The top 5 enrolling centers each will count as a separate group and all other centers will be combined into a sixth catchall group. So there will be a total of 6 center groups.

The standardized log odds ratio estimate for treatment arm from this model will be used as the test statistic (Z-statistic) and will be compared to the futility boundary in Table 1. The futility boundaries were obtained from the Gamma family spending function with shape parameters of -8.

Futility Interim Analysis Stopping Boundary

Table 1: Group Sequential Design Stopping Thresholds for Primary Endpoint: Primary Analysis Approach

Analysis	Information Fraction	Sample Size	Futility Boundary for Z-Statistic	Efficacy Boundary for Z-Statistic
Interim	0.56	76	-0.31	-
Final	1.00	136	-	1.96

Sensitivity Analysis for Interim Analysis

A sensitivity analysis will be conducted ONLY IN THE EVENT that the primary analysis reaches its futility boundary at the interim analysis as above mentioned in Table 1.

The sensitivity analyses would include 62 participants at interim analysis. Due to a process error that has been corrected, there is a small chance that the treatment assignments of some participants were unblinded to their treatment center staff. A maximum of 14 participants could have been affected. To assess the robustness of the primary analysis results in consideration of this, a sensitivity analysis will be conducted where these 14 participants will be omitted from the ITT analysis population. Therefore, the sensitivity analysis will include 62 subjects (76 randomized – 14 randomized subjects potentially affected)

The efficacy and futility boundaries for the sensitivity analyses are displayed in **Table 2**. Again, the futility boundaries were obtained from the Gamma family spending function with shape parameters of -8.

Table 2: Group Sequential Design Stopping Thresholds for Primary Endpoint: Sensitivity Analysis Approach

Analysis	Information Fraction	Sample Size	Futility Boundary for Z-Statistic	Efficacy Boundary for Z-Statistic
Interim	0.51	62	-0.61	-
Final	1.00	122	-	1.96

If the Z-statistic from the primary analysis is less than or equal to the futility boundary, a sensitivity analysis will be conducted that excludes from the ITT population the 14 participants who could have potentially been affected by unblinding. Similarly, this analysis would use a logistic mixed model and the standardized log odds ratio estimate for treatment arm would be used as the test statistic and compared to the futility boundary in Table 2.

Results and Data Presentation to DSMB

Primary results for the interim analysis will be presented as below:

Analysis	Information Fraction	Sample Size (#Patient Included)	Test Statistic	Reach Futility Boundary for Z-Statistic (Yes or No)
Interim	0.56	76		

Sensitivity analysis results for the interim analysis will be presented as below:

Analysis	Information Fraction	Sample Size (#Patient Included)	Test Statistic	Reach Futility Boundary for Z-Statistic (Yes or No)
Interim	0.51	62		

If both the primary and sensitivity analysis results meet their corresponding futility boundaries, the study team recommends closure of the trial. Otherwise, if one or both of the analyses do not meet their futility boundaries, the team recommends that the trial continue.

Besides the interim analysis results, below exhibits will also be included in the DSMB report to facilitate the review, and these are usually included in the regular DSMB closed data review. All data will be presented in **Closed** session by the Unblinded STAT lead.

Exhibit R1: Participant disposition table

Numbers of patients that were randomized, received study treatment, completed study treatment, stopped study treatment early, withdrew by treatment arm I and II

Exhibit R2: Overall response

- (A) Overall response by Day 56 in Arm I
- (B) Overall response by Day 56 in Arm II

Overall (complete + partial) response summarized at Days 14, 28, and 56

Timing of Interim Analysis

From operation perspective, DCC is monitoring the data submission for the enrolled patients to ensure we have 76 randomized patients with Day 28 evaluation for the primary endpoint for this interim analysis. A nightly monitoring is put in place and will send an automatic email alert to the STAT team when the time is approaching to see the data submission for the primary endpoint for the first 76 patients. Patient who would expire prior to Day 28 will be included in the ITT population for the primary endpoint. DCC will plan a data freeze for DSMB review when 76 patients reach 28 days follow up.

Signature Page

CSL964_5001 - Statistical Analysis Plan - 30 November 2023

Signed By	Date (GMT)
PPD	08-Feb-2024 23:33:39
Approved PPD	

Signature Page 1 of 1

--- Do Not Detach This Signature Page ---
